4.0 TRIAL DESIGN

4.1 Overview of Trial Design

Treatment will be administered on an outpatient basis but may be administered in the inpatient setting for patients who are hospitalized and meet criteria for study enrollment. No investigational or commercial agents or therapies other than those described below may be administered with the intent to treat the patient's disease under study.

Monotherapy Cycle

There is a 7-day monotherapy cycle where patients receive APR-246 IV on Day 1 and APR-246 PO on Day 2. The primary purpose of the monotherapy cycle is to obtain peripheral blood for monotherapy PK and PD analyses following IV and PO administration of APR-246.

Patients will start treatment with APR-246 IV as a single agent administered on Day 1 of a single 7-day monotherapy cycle at the assigned cohort dose level, prior to Cycle 1 Day 1 of combination therapy. On Day 2 of the 7-day monotherapy lead-in period, patients will receive a single dose of APR-246 administered PO at the dose of 500 mg. After review of oral PK data from at least 6 patients, a decision can be made whether to increase the PO dose of APR-246 and/or administer APR-246 with a standard high-fat meal to investigate, respectively, dose linearity in PK and/or the effect of food on oral absorption of APR-246. Dose escalation of the oral dose or switching to administration with food will be determined by PK to ensure that the APR-246 exposure levels after oral dosing do not exceed the exposure levels after IV administration in terms of C_{max} and AUC.

Combination Treatment

After the APR-246 monotherapy lead-in, study treatment will consist of APR-246 administered as an IV infusion at the same assigned dose that was used during the monotherapy lead-in period once weekly, on Days 1, 8 and 15 of each cycle, concurrently with venetoclax for the 5-week ramp-up at the dose of 20 mg during Week 1, 50 mg during Week 2, 100 mg during Week 3, 200 mg during Week 4, and 400 mg during Week 5. Beginning Cycle 2 Day 1, venetoclax will be administered at 400 mg (or tolerable dose following 5-week ramp up) PO daily. IV rituximab will be initiated at 375 mg/m² on Cycle 2, Day 2 and then administered at 500 mg/m² on Day 2 of Cycles 3-7. After 6 cycles of treatment with APR-246 in combination with venetoclax + rituximab, APR-246 + venetoclax will continue to be

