administered starting at Cycle 8 for up to a total of 24 cycles. Cycle 1 will consist of 35 days. Cycles 2 and beyond will be 28 days. The safety assessment (DLT) period begins at the start of treatment and extends to the end of Cycle 3.

Patients with RT will receive APR-246 administered IV at the assigned cohort dose with standard doses of venetoclax and rituximab. Dose escalation will proceed in a standard 3 + 3 dose escalation design.

The intended three dose levels of APR-246 are: 1.5 g/day, 3.0 g/day, and 4.0 g/day administered as an IV infusion over 6 hours. The dose escalation will proceed until a pharmacologically active dose level is achieved. It will be stopped if the maximum tolerated dose (MTD) is reached at a dose level below the maximum planned dose of 4.0 g/day. For the determination of MTD the following rules will be applied:

- Three patients will be enrolled to Dose Level 1.
- If 0 patients out of 3 experience a DLT at Dose Level 1 (1.5 g/day of APR-246), the dose will advance to the next level (Dose Level 2, 3.0 g/day).
- If 1 of the first 3 patients at Dose Level 1 experiences a DLT, 3 additional patients will be recruited and treated at the same dose level (1.5 g/day of APR 246).
- If ≥ 2 patients out of 3-6 patients in a cohort experience a DLT at Dose Level 1 (1.5 g/day of APR-246), the study will temporarily discontinue enrollment and the Data Review Team (DRT) will consider further enrollment and possible dose/schedule adjustments.
- If < 2 patients out of 6 experiences a DLT at Dose Level 1 (1.5 g/day), dose escalation will proceed to the next cohort level (Dose Level 2, 3.0 g/day).
- For each cohort, if there are 0 DLTs in the first 3 patients enrolled, the cohort will advance to the next level. If there is 1 DLT in the first 3 patients enrolled to a cohort, the cohort will enroll an additional 3 patients. If there are ≥ 2 DLTs in a cohort, the prior lower dose level will be declared the MTD.
- If there are ≤ 1 DLT in the first 3 patients enrolled at Dose Level 3, 4.0 g/day APR-246, the study will enroll 3 additional patients at Dose Level 3. If there are ≤ 1 DLTs in 6 patients enrolled at Dose Level 3, 4.0 g/day APR-246 will be declared the MTD.

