Upon determination of the pharmacologically active dose or MTD, or when the maximally intended dose is reached, up to 10 additional patients may be enrolled at this dose level to confirm the assessment and to collect additional safety, PK and PD data to aid in determining the recommended dose of APR-246 in combination with venetoclax and rituximab.

Table 3. APR-246 Dose Levels

Dose Modification	APR-246 Dose
Dose Level 1	APR-246 1.5 g/day 0.5 g (for first 45 minutes) + 1.0 g (for 5 hours 15 minutes)
Dose Level 2	APR-246 3.0 g/day 1.0 g (for first 45 minutes) + 2.0 g (for 5 hours 15 minutes)
Dose Level 3	APR-246 4.0 g/day 1.33 g (for the first 45 minutes) + 2.66 g (for 5 hours 15 minutes)

Prior to initiation of study treatment with APR-246 administered IV in combination with venetoclax and rituximab (during treatment cycles 2-7), patients will receive APR-246 alone on Day 1 and Day 2 of the 7-day monotherapy lead-in period, during which PK and PD of APR-246 following IV and PO administration will be evaluated. On Day 1 of the monotherapy lead-in period, APR-246 will be administered IV at the assigned cohort dose. On Day 2, APR-246 will be administered PO at the dose of 500 mg. This dose may be increased based on emerging PK data to determine dose linearity after oral dosing. Patients will be required to fast for at least 10 hours prior to APR-246 PO administration. Furthermore, a sub-group of patients may receive an oral dose of APR-246 in combination with a standard high-fat meal to determine the effect of food on APR-246 absorption.

Additional dose levels may be explored if warranted based on emerging DLT, safety, PK, and/or PD data. In addition, patients who have received at least 3 cycles of therapy at the assigned dose cohort level may advance to the next higher dose level once the next higher dose level has been declared safe by the DRT.

Responses will be assessed according to response criteria for RT ([Appendix V](#)) via blood, BM, and imaging (positron emission tomography [PET]/computed tomography [CT]). Response assessments are to be performed every 3 cycles and PET-CT scanning is recommended. For patients who achieve CR, imaging may be omitted, and minimal residual disease (MRD) assessment will be completed using flow cytometry and/or molecular techniques from the BM and/or peripheral blood.

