7.4 Pharmacokinetic and Pharmacodynamic Evaluation

APR-246 will be administered in a 7-day monotherapy cycle on Days 1 and 2, via IV and PO route, respectively. PK samples for APR-246 measurements will be taken on Day 1 pre-dose, at the end of the infusion and 1, 2 and 4 hours after the end of the infusion, and 24 hours after the end of the infusion prior to APR-246 PO administration on Day 2, as well as 0.5, 1, 1.5, 2, 3, 4, 6, 10 and 24 hours after the oral administration on Day 2. Following review of the initial PK profiles after oral administration, the PK sampling scheme will be reviewed and optimized. Unnecessary samples will be removed from the schedule and sampling times changed (the total number of samples specified below will not be exceeded).

Blood samples for PD markers and GSH will be collected as follows: on Day 1 pre-dose and 4 hours after the end of the infusion; on Day 2 prior to oral administration as well as 10 and 24 hours after the oral administration.

In addition, blood samples for PD and GSH markers will be collected on Cycle 1 Day 1 pre-dose and 4 hours after the end of the infusion.

Table 18: PK, PD, and Glutathione Blood Sampling Timepoints for APR-246

PK and PD Blood Sampling Timepoints	APR-246 PK and PD Sample Collection										
	APR-246 Monotherapy Lead-In Period						Cycle 1	Cycle 2		Cycles 3+	
	D1 ^a		D2 ^b		D3		D1	D 1	D 8	D 15	D1
	PK	PD	PK	PD	PK	PD	PD	PK	PK	PK	PK
Prior to APR-246 administration ^{b,c}	×	× ^d	× ^b	× ^d	× ^c	× ^d	× ^d	×	×	×	
After APR-246 administration (<5 min after end of IV infusion [EOI])	×							×	×	×	×
0.5 h after APR-246 administration			×								
1 h (±5 min) after APR-246 administration	×		×					×	×	×	
1.5 h (±5 min) after APR-246 administration			×								
2 h (±5 min) after APR-246 administration	×		×								
3 h (±15 min) after APR-246 administration			×								
4 h (±15 min) after APR-246 administration	×	× ^d	×				× ^d				
6 h (±15 min) after APR-246 administration			×								
10 h (±1 h) after APR-246 administration			×	× ^d							

^a PK samples are collected at time points related to IV administration of APR-246 on Day 1 of monotherapy lead-in period

^b PK samples are collected at time points related to PO administration of APR-246 on Day 2 of monotherapy lead-in period with the exception of the pre-dose sample collected 24 h after IV administration of APR-246 on Day 1 (prior to PO administration of APR-246 on Day 2)

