8.9 Pharmacokinetic Analysis

Concentrations of APR-246 will be determined using validated bioanalytical methods.

During the APR-246 monotherapy cycle, PK sampling for APR-246 will be performed on Day 1 and 2. Noncompartmental PK analysis will be used to determine C_{max} , T_{max} , AUC and bioavailability after oral dosing for decision making on dose escalation of the oral dose.

PK sampling for APR-246 will be performed during Cycle 2, on Day 1, 8 and 15 and on Day 1 from Cycle 3 onwards.

PK sampling for venetoclax and rituximab will not be performed for this study.

The PK of APR-246 will be summarized using descriptive statistics (mean, standard deviation, CV% mean, geometric mean, CV% geometric mean). The concentration data for APR-246 will be evaluated using (popPK analysis in combination with data from other studies.

APR-246 AUC and C_{max} will then be tested for association with signs of efficacy and safety. If an observable trend exists, a PK/PD model will be developed to evaluate the exposure-response relationship between APR-246 plasma exposure and outcome measures. Demographic and clinical

data (ethnicity, current age, body weight, sex, disease status, etc.) will be utilized to assess interpatient variability in the PK and PK/PD relationships.

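### No APR-246 sample is drawn during the two-rate 6-hour lead-in infusion: the noncompartmental 0–6 h IV area is understated, and the net bias in AUC, F and CL depends on choices the plan leaves open

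*Combined protocol and SAP*

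**What the plan says.** Section 4.1 describes APR-246 as "administered as an IV infusion over 6 hours". Table 3 splits Dose Level 1 as "0.5 g (for first 45 minutes) + 1.0 g (for 5 hours 15 minutes"; the other two levels use the same one-third to two-thirds split.

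Section 7.4 schedules the lead-in Day 1 samples "taken on Day 1 pre-dose, at the end of the infusion and 1, 2 and 4 hours after the end of the infusion". The last IV sample is "24 hours after the end of the infusion prior to APR-246 PO administration on Day 2" in the text, but Table 18 footnote b calls it the "pre-dose sample collected 24 h after IV administration of APR-246 on Day 1". Oral samples follow "as well as 0.5, 1, 1.5, 2, 3, 4, 6, 10 and 24 hours after the oral administration on Day 2". Table 18 has no row for a draw during an infusion, on this day or in any later cycle. Section 7.4 lets sampling times change after the first oral profiles have been reviewed, without raising the total number of samples.

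Section 8.9 uses noncompartmental analysis for Cmax, Tmax, "AUC and bioavailability after oral dosing for decision making on dose escalation of the oral dose". It sends the APR-246 concentrations to a population PK analysis as well. It names no trapezoidal rule and does not say which method supplies IV CL and Vd. Under Section 4.1, any increase of the oral dose must ensure that oral exposures "do not exceed the exposure levels after IV administration in terms of" Cmax and AUC. Section 8.3.2 lists IV Cmax, AUC, Vd and CL, and oral F, as secondary endpoints.

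**The concern.** The Day 1 IV profile is the reference for F and for the oral exposure ceiling. With no sample between pre-dose and end of infusion (EOI), the trapezoid joins zero to the 6-hour value with a straight line. The true curve rises steeply during the load and then bends, so it lies above that line. The lost area sits in the IV denominator of F and would remain even with complete washout before the oral dose. IV Cmax is also read only at EOI or later. If the drug distributes quickly, or is eliminated very quickly, the highest concentration could fall at 45 minutes, where there is no sample. At stake are the estimates of IV AUC, F and any noncompartmental CL, and possibly IV Cmax.

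**Working it through.** The plan states no AUC, CL or F figure, so there is none to reproduce. The APR-246 half-life is redacted; half-lives of 2–8 h are assumed as a range.

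**Inputs.** Table 3, Dose Level 1: 0.5 g / 0.75 h = 0.667 g/h, then 1.0 g / 5.25 h = 0.190 g/h, a ratio of 3.5. IV times from the start of infusion: 0, 6, 7, 8 and 10 h, then 30 h (text of Section 7.4) or 24 h (one reading of footnote b).

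**Model.** One compartment, with dose and volume set to 1 and k = ln 2 / half-life. The rates are R1 = (1/3)/0.75 = 0.4444 and R2 = (2/3)/5.25 = 0.1270.

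- C(0.75) = (R1/k)(1 − e^(−0.75k))
- C(6) = C(0.75)e^(−5.25k) + (R2/k)(1 − e^(−5.25k)), then exponential decline
- True total AUC = 1/k; true 0–6 h area = (1 − C(6))/k
- Trapezoid 0–6 h = ½ × 6 × C(6) = 3 C(6)

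**Worked case, half-life 4 h** (k = 0.1733). C(0.75) = 0.3126 and C(6) = 0.5636.

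- 0–6 h: 3 × 0.5636 = 1.691 against a true 2.518, ratio 0.671.
- Log-down tail (exact for one compartment): 1.691 + 0.5636/0.1733 = 4.943 against a true 5.771, ratio 0.857.
- Linear, last sample 30 h: 1.691 (0–6) + 1.635 (6–10) + 2.906 (10–30) + 0.051 (extrapolated) = 6.283, ratio 1.089. The true 10–30 h area is 1.575, so the straight line over that gap adds 1.331. That more than offsets the 0.827 lost during the infusion.
- Linear, last sample 24 h: 1.691 + 1.635 + 2.147 + 0.144 = 5.617, ratio 0.973.

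**Estimated / true, schedule as written:**

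| Half-life (h) | 0–6 h area | Total, log-down | Total, linear, 30 h | Total, linear, 24 h | C(0.75)/C(6) |
|---|---|---|---|---|---|
| 2 | 0.571 | 0.723 | 0.948 | 0.857 | 0.83 |
| 3 | 0.633 | 0.808 | 1.065 | 0.947 | 0.64 |
| 4 | 0.671 | 0.857 | 1.089 | 0.973 | 0.55 |
| 6 | 0.716 | 0.908 | 1.065 | 0.979 | 0.47 |
| 8 | 0.741 | 0.933 | 1.036 | 0.977 | 0.44 |

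**CL and F.** Noncompartmental CL = dose/AUC, so its bias is the inverse: 7–38% high with log-down, from 8% low to about 6% high with linear and 30 h, 2–17% high with linear and 24 h. For F, the oral profile was simulated at the protocol's oral times (assumed absorption rate 1.5/h, true F = 1, no IV carry-over). Estimated F is 1.07–1.36, 0.99–1.13 and 1.06–1.25 respectively.

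**Peak.** In one compartment C(0.75)/C(6) is 1.40 at a half-life of 1 h and 1.02 at 1.5 h. It is below 1 throughout the table, so there the peak is at EOI, which is sampled.

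**Two compartments.** Across five illustrative parameter sets the 0–6 h area was 36–49% low. Total AUC was 10–30% low with log-down, 2–23% low with linear and 30 h, and 7–27% low with linear and 24 h. In two of the five sets the peak came at 45 minutes, and EOI read 10% and 22% below it.

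**Adding samples at 0.75 h and 3 h (one compartment), total estimated / true:**

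| Half-life (h) | Log-down | Linear, 30 h | Linear, 24 h |
|---|---|---|---|
| 2 | 0.994 | 1.219 | 1.129 |
| 3 | 0.994 | 1.251 | 1.133 |
| 4 | 0.995 | 1.227 | 1.112 |
| 6 | 0.997 | 1.154 | 1.069 |
| 8 | 0.998 | 1.101 | 1.042 |

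**The case against.** A reader might infer that IV AUC is biased low, and F and CL high, in every patient. The documents do not support that. They name no trapezoidal rule, and with linear trapezoids and a 30 h last sample the error in total AUC changes sign, because the long gap after 10 h overstates the tail. This does not vindicate the schedule, since two errors merely offset each other, but it rules out a one-sided claim for the total.

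A reader might also infer that a peak at 45 minutes is being missed. That needs a half-life of about 1.5 h or less, or marked distribution, and the human PK section that would settle it is redacted. All that can be said is that the schedule could not show such a peak.

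Two further points for the plan stand. Population PK fits the known dosing history and has no 0–6 h trapezoid. Section 8.9 places the exposure-response work after it, and the plan does not say that CL and Vd come from the noncompartmental analysis. And IV exposure serves as a ceiling: if it is understated, the oral limit becomes stricter, not looser.

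What the objection does not remove is that Section 8.9 assigns the bioavailability behind the oral-dose decision to noncompartmental analysis. Nor is the promised review of sampling times an answer: it follows the oral profiles, and an unsampled phase cannot reveal its own gap.

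**Conclusion.** The point holds in a limited form. The noncompartmental 0–6 h IV area is too low in every scenario run: 26–43% low in one compartment at half-lives of 2–8 h. The net error in total IV AUC at those half-lives ranges from 28% low to 9% high. Its size, and under the linear rule its sign, depend on the half-life, the trapezoidal rule and whether the last sample is at 24 or 30 h. The plan leaves the last two open. An unseen early peak is a possibility, not a finding. The harm is to the estimates of AUC, F, any noncompartmental CL and possibly Cmax, not to the safety of the oral ceiling. All magnitudes rest on assumed kinetics. The change is worth making because it is cheap.

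**What to change.** 1. In Section 8.9, derive IV AUC, CL, Vd and F from a compartmental or population PK fit that uses the recorded two-rate infusion. If noncompartmental analysis is kept, specify linear-up/log-down. State which method supplies each parameter.
2. In Section 7.4 and Table 18, add lead-in Day 1 samples at the end of the 45-minute load and about 3 h into the infusion. Drop two post-oral draws (for example 1.5 h and 3 h) to stay within the sample ceiling. Do not add these samples under a linear trapezoid alone: total AUC would then be about 10–25% high with a 30 h last sample, or 4–13% high with 24 h. With log-down the one-compartment error falls to 1% or less.
3. Reconcile the two descriptions of the last IV sample in Section 7.4 and Table 18 footnote b.

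The cost is two moved draws on a day when vital signs are already taken 2 h into the infusion, plus wording. The downside is slightly fewer points around the oral peak, and oral Cmax and Tmax are themselves secondary endpoints; which two draws to give up is therefore a judgement for the sponsor.

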7.5 Electrocardiographic Assessment

[Table 19](#) describes the routine ECG requirements.

Table 19. ECG Assessment Requirements

Time Point	ECG, number	Timing
Baseline/Screening	TriPLICATE	Within 28 days of study treatment ¹
APR-246 Monotherapy Lead-In	TriPLICATE	Pre-dose; at the end of the infusion (± 30 min) ²
Cycle 1, Day 1, 8 and 15	TriPLICATE	Pre-dose; at the end of the infusion (± 30 min)
Cycles 2+, Day 1	TriPLICATE	Pre-dose; at the end of the infusion (± 30 min)
End of Treatment	TriPLICATE	Within 28 days of the last dose of APR-246

¹ Baseline/Screening registration is for eligibility purpose and should be performed before the patient is approved and registered in IWRS to start any treatment on study, i.e., 28 days prior to the first dose of venetoclax in ramp-up.

² On Day 2 of the APR-246 monotherapy lead-in period, ECG is obtained prior to PO administration of APR-246, and then 6 hours after APR-246 administration.

If repeated QTcF measurements show a stable QTcF < 470 msec, unless due to BBB and/or pacemaker, with no significant change at the EOI during several cycles of treatment, reducing the number of ECGs performed in the study may be discussed with the Medical Monitor.

If a patient starts treatment with another medication known to prolong QT interval at any time during the study therapy, an additional pre- and post-dose (6 hours after start of infusion, ± 30 min) ECG should be performed on the next treatment day.

Please consult Section [5.3.1](#) for additional requirements for proceeding with treatment with APR-246.

8.0 STATISTICS

Continuous variables will be presented by n , mean, median, standard deviation and range (minimum and maximum), and categorical variables will be presented by count and percentage of patients as appropriate. Data will be presented by dose escalation cohort. All patient data, efficacy and safety data will be summarized and listed.

8.1 Sample Size

A total of up to 48 evaluable patients will be included in the study.

Patients with RT will be enrolled and receive APR-246 at the assigned dose cohort level. Dose escalation will proceed in a 3 + 3 design. Cohorts will consist of 3-6 patients and 10 additional patients may be enrolled at the MTD. Approximately 6 + 6 + 6 (18) DLT evaluable patients will be enrolled. In the event Dose Level 3 is declared the MTD, up to 10 additional patients may be enrolled at Dose Levels 1 and 2 to gain additional safety, PK, and/or PD data to help define the recommended dose of APR-246 in this combination.

8.2 Analysis Populations

Safety population: Patients will be evaluable for safety if they receive at least one dose of APR-246. The safety population will be the primary analysis population used for all analyses such as patient disposition, patient demographics, exposure, safety parameters and efficacy parameters. The safety population will be the primary analysis population for efficacy.

Efficacy evaluable (EE) population: All patients who complete at least one treatment cycle of APR-246 and venetoclax and rituximab and who have at least one post-treatment clinical response assessment. The EE population will be the secondary analysis population for efficacy.

PD population: Patients will be evaluable for PD if at least one sample for PD evaluation has been obtained after administration of APR-246.

PK population: Patients will be evaluable for PK if at least one sample for PK evaluation has been obtained.

8.3 Endpoints

8.3.1 Primary

1. PD analysis of circulating peripheral blood cells to determine effects of APR-246 on cellular viability and apoptosis.
2. Frequency of TEAEs and SAEs related to APR-246 in combination with venetoclax and rituximab therapy.
3. The highest tested dose of APR-246 with acceptable toxicity (the dose producing <33% of DLT).

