7.1.2 Reporting of Adverse Events

7.1.2.1 Adverse Events

An AE is any untoward medical occurrence in a patient administered a pharmaceutical product that does not necessarily have a causal relationship with the treatment. An AE can be any unfavorable and unintended sign (including a laboratory finding), symptom or disease temporally associated with the use of a medicinal (investigational) product, whether or not related to the medicinal (investigational) product.

The AE reporting period starts at the time of study treatment initiation. For the time period from signing of informed consent up to receipt of the first dose of APR-246, non-serious events should be recorded as medical history on the appropriate eCRF page within the clinical database. SAEs that occur during the screening period are required to be reported and should include an assessment on whether the SAE was related to a protocol-defined procedure or activity. AEs will be collected for up to 30 days after the last dose of study treatment, unless the patient has withdrawn consent for study participation or started a new anti-cancer treatment for the disease under study, whichever occurs first. Hospitalization to start new anti-cancer treatment for primary disease after confirmed progression/relapse does not meet criteria for AE or SAE.

Progression of primary disease and events unequivocally related only to progression of primary

disease do not need to be reported on the AE CRF page. Progression of primary disease should be reported on a response assessment eCRF.

At each evaluation, patients should be interviewed in a non-directed manner to elicit potential adverse reactions from the patient. The occurrence of an AE will be based on changes in the patient's physical examination, laboratory results, and/or signs and symptoms.

All AEs (except laboratory abnormalities that are assessed as not clinically significant by the Investigator), regardless of causal relationship, are to be recorded in the eCRF and source documentation. The Investigator must determine the intensity of any AEs according to the NCI CTCAE version 5.0 and their causal relationship to each study medication administered that has been administered to the patient at the time of event onset. Those AEs not covered by these criteria will be graded as follows:

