8.6 Safety

Safety data will be summarized for the safety population. These data will include AEs, laboratory parameters, electrocardiogram, and physical exam findings. AE terms will be coded using the Medical Dictionary for Drug Regulatory Activities (MedDRA)®, version 22.0 or higher. AEs will be summarized by SOC, preferred term, severity, and relationship to treatment. SAEs, deaths, and AEs leading to early discontinuation of study treatment will be summarized. Laboratory parameters will be summarized by maximum NCI-CTCAE version 5.0 severity grade and also by change from pre-treatment to scheduled time points using descriptive statistics. Laboratory parameter listings will include the normal ranges for each parameter. Each value will be classified as falling above, below, or within the normal range.

Only SAEs related to study screening procedures from the time of signing informed consent and AEs from the time of first dose of APR-246, throughout study enrollment, and up to 30 days after last dose of study treatment are to be collected. Data summaries will include only TEAEs, defined as events occurring at the start of APR-246 infusion in the monotherapy lead-in or Cycle 1, Day 1 up to and including 30 days after last dose of study treatment.

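### Primary endpoint 2 is a crude percentage of patients with TEAEs/SAEs by cohort, over observation times that can run from about a month to nearly two years; common-window, exposure-adjusted and by-phase summaries should be added.

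*Combined protocol and SAP*

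**What the plan says.** Section 8.3.1 lists three primary endpoints. The second is "Frequency of TEAEs and SAEs related to APR-246 in combination with venetoclax and rituximab therapy", with no time window and no exposure denominator.

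Section 8.0 sets the summary measure and the grouping: "categorical variables will be presented by count and percentage of patients as appropriate", and "Data will be presented by dose escalation cohort". Section 8.6 adds that "AEs will be summarized by SOC, preferred term, severity, and relationship to treatment". It limits data summaries to TEAEs, counted from the start of APR-246 "up to and including 30 days after last dose of study treatment". Section 7.1.2.1 stops AE collection earlier in some cases: "unless the patient has withdrawn consent for study participation or started a new anti-cancer treatment".

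Entry to the analysis needs very little treatment: "Patients will be evaluable for safety if they receive at least one dose of APR-246" (Section 8.2). At the other end, Section 4.1 has APR-246 plus venetoclax "administered starting at Cycle 8 for up to a total of 24 cycles".

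Section 8.2 lists exposure among the analyses on the safety population, but nothing uses it as a denominator for TEAEs. The exposure-response analysis in Section 8.9 uses APR-246 AUC and Cmax, not time at risk.

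**The concern.** A crude cumulative percentage can only stay level or rise as a patient is watched for longer. If cohorts differ in time on treatment, their percentages differ even when the monthly risk is the same, and a table by dose mixes toxicity with duration.

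Two features add to this. The single percentage pools APR-246 alone, APR-246 with venetoclax, and the triple combination, although the endpoint is worded for the last of these. In addition, patients may move to the next dose level after at least 3 cycles (synopsis, Treatment Plan; Section 4.1). Summarised by assigned cohort, their later events would be shown against a dose they no longer receive.

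At stake is how one of three primary endpoints is read. Under Section 5.1.5 the Data Review Team also weighs the accumulated safety data when it advises on the optimal dose.

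**Working it through.** **1. The plan's own figures.**
- Sample size: 6 + 6 + 6 in escalation, 10 at the MTD, and 10 each at Dose Levels 1 and 2 = 48, as stated in Section 8.1. A dose level can therefore hold 3 to 16 patients. The plan makes no power calculation, and it gives no event rates.
- DLT period: Section 5.1.4 and the synopsis state 7 + 84 = 91 days. Section 4.1 gives 35 days for Cycle 1 and 28 for later cycles, so lead-in plus Cycles 1-3 is 7 + 35 + 28 + 28 = 98 days. The two do not agree.

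**2. Treatment phases** (lengths from Section 4.1; rituximab cycles from Section 5.1.3).

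| Phase | Drugs | Days |
|---|---|---|
| Lead-in | APR-246 | 7 |
| Cycle 1 | APR-246 + venetoclax ramp-up | 35 |
| Cycles 2-7 | APR-246 + venetoclax + rituximab | 6 × 28 = 168 |
| Cycles 8-24 | APR-246 + venetoclax | 17 × 28 = 476 |
| Total | | 686 |

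These are four phases but three drug combinations. Rituximab starts on Cycle 2 Day 2, which is study day 7 + 35 + 2 = 44.

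**3. Range of observation.**
- Longest: 686 + 30 = 716 days, or 23.5 months at 30.4375 days per month.
- Other readings are longer. Venetoclax for a full two years (Section 4.4) gives 7 + 730 + 30 = 767 days. Reading the 24 cycles as additional from Cycle 8 gives 7 + 35 + 168 + 672 + 30 = 912 days. Table 17 shows venetoclax through Cycle 24, which favours 716.
- Shortest: one dose gives 1 + 30 = 31 days, and less if consent is withdrawn or new therapy starts.

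**4. Effect on a crude percentage, same hazard in both cohorts.** With constant hazard h and fixed observation T, the percentage is 1 − exp(−hT). Both h (per month) and T (3 and 10 months) are assumptions.

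| h | 3 months | 10 months |
|---|---|---|
| 0.05 | 14% | 39% |
| 0.10 | 26% | 63% |
| 0.20 | 45% | 86% |

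**5. Variable time on observation.** Let time on observation be exponential with mean m months, capped at 23.5. The crude percentage is h/(h + 1/m) × [1 − exp(−(h + 1/m) × 23.5)]. The last column is 1 − exp(−h × 98/30.4375), the incidence to the end of Cycle 3 with early exits accounted for.

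| h | Crude, m = 3 | Crude, m = 9 | To day 98, either cohort |
|---|---|---|---|
| 0.02 | 5.7% | 14.6% | 6.2% |
| 0.05 | 13.0% | 30.3% | 14.9% |
| 0.10 | 23.1% | 47.0% | 27.5% |
| 0.20 | 37.5% | 64.2% | 47.5% |

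Under these assumptions the order can even reverse. A dose with h = 0.10 and m = 3 shows 23.1% crude, against 30.3% for a dose with half the hazard and m = 9. The common window gives 27.5% v 14.9%.

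**6. Precision.** Exact 95% intervals are 4% to 78% for 2 of 6 and 25% to 75% for 8 of 16.

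**The case against.** The strongest reply is that dose decisions do not rest on this table. Escalation and the MTD use DLTs over the lead-in and Cycles 1-3, and primary endpoint 3 is built on them. Section 5.1.5 and the synopsis define the recommended dose by apoptosis of circulating malignant cells in the monotherapy cycle, at or below the MTD or maximum dose. This stands. A reader might infer that the plan could pick the wrong MTD or recommended dose through this bias, but the documents do not support that. The remaining route is the Data Review Team's judgement on the accumulated safety data.

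It is also true that the TEAE summary is descriptive. No test between doses is planned, and exposure, AE dates and listings will be available. That makes the remedy cheap, but a primary endpoint should not leave the reader to rebuild its denominator from listings.

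The size is hypothetical: neither the hazards nor the durations come from the plan. The ratio of 716 to 31 days compares two extreme individuals, not cohort averages. Section 2.1 cites median survival of 3 to 11 months, so few patients may reach 24 cycles. For events clustered early, such as tumor lysis in the ramp-up or first-infusion reactions, the distortion is small. In cohorts of six, sampling error is larger than most of the differences shown: 2/6 v 4/6 gives a two-sided Fisher p of about 0.57. All of this limits the weight of the point but does not remove a systematic error.

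Two further readings go too far. The documents do not show that a more active dose will keep patients on treatment longer; this is plausible, and unequal time on treatment from any cause is enough. Nor is counting lead-in and Cycle 1 events a mistake, since Section 8.6 includes the lead-in on purpose. The fault is that one percentage under the name of the triple combination does not separate them.

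**Conclusion.** The point holds as a limit on the interpretation of primary endpoint 2 and on the team's reading of accumulated safety data. It does not reach the 3+3 rule, the MTD or the definition of the recommended dose.

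The direction follows from arithmetic: at equal hazard, longer observation gives a higher crude percentage whenever risk continues beyond the shorter period. The size depends on assumed constant hazards of 0.05 to 0.20 per month and assumed observation of 3 v 10 months. It matters most for outcomes that accrue over time, such as SAEs, infections and cytopenias. It matters little for early-clustered events, or for any-TEAE if nearly every patient has one. The reversal in the working shows what is possible, not what this trial should expect.

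**What to change.** In Section 8.6, keep the crude table and add by dose level:

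- **Common window.** Cumulative incidence of first TEAE and first SAE from first dose to the end of Cycle 3. State in advance whether patients who leave earlier are censored or counted as competing events; a plain percentage at that point would still be biased by early exits.
- **Whole period.** Event rates per 100 patient-months, with events and person-time assigned to the dose received at onset rather than the assigned cohort.
- **Phase.** Tables for lead-in, Cycle 1, Cycles 2-7 and Cycle 8 onward, so that events under the triple combination can be seen separately.

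Define the window as the end of Cycle 3, and reconcile the 91 days in the synopsis and Section 5.1.4 with the cycle lengths in Section 4.1, which give 98 days with the lead-in.

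The cost is analysis wording and a few descriptive tables from AE dates and dosing records already collected. The added figures will be imprecise with 3 to 16 patients per dose level and should be shown with intervals.
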